Linear mixed effects models were used to estimate the effects of OST-T2 on outcomes. Models had three levels: assessment time nested within student and students nested within school. All models included time (as splines), treatment, and time-by-treatment interactions. Mixed effects models included random intercepts for school (to account for clustering of students within schools), random slopes (over time) to allow for different trajectories across schools, and a random intercept and random slope for student to allow for variation in the effect of treatment assignment across students over time. Modeling for the clustering effect of schools accounted for more than one student being rated by multiple teachers; teachers rated a mean of 1.6 students and approximately 85% of teachers rated three or fewer students at each time point. Statistical significance was evaluated using a threshold p value of .0083, accounting for the estimation of three contrasts of time-by-treatment differences per outcome and two measures per domain (OTMP skills [COSS-P, COSS-T], homework performance [HPC, HPQ-T], and academic performance [ACES, APS]).

Mixed effects models facilitated both the graphic display, and contrasts, of curves depicting the expected values of outcomes over time from time zero until 12-month follow-up for the student with the last data collected. All confidence bounds reflected variances based on the multi-level linear model. To evaluate differences between conditions, we estimated model-based, expected values for outcomes at four preplanned times, 0 (baseline), 14 (post-treatment), 22 (5-month follow-up) and 55 (12-month follow-up) weeks, except for academic grades, which

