were estimated for beginning and end of school year. Those actual times were translated into their equivalent values in the models for restricted cubic splines. Expected values were then the product of these times and estimated coefficients from the mixed effects models. The primary overall estimate of intervention effect for each outcome was the between-group difference of the change in expected values (means) from time zero to the prespecified outcome assessment times. The mixed effects models applied in this study assume that missing scores were missing at random, a reasonable assumption given that we also adjusted for student baseline covariates that might explain missed assessments. Analyses used all available scores, consistent with an ITT approach. Sensitivity analyses were conducted to determine whether data collected after the school shutdown due to the COVID-19 pandemic (March 16, 2020) altered study findings.

Mixed effects models were also used to estimate student-level outcomes at each assessment time. We estimated random effects for students and schools to determine model-based estimates, which reflect expected values (average score of the entire group) plus individual random effects (departures of the individuals from average). Statistical theory suggests that model-based predictions provide better estimates of true values than the actual data. Model-based predictions, called “empirical Bayes” estimates, combine individual measures with group-level expected values in a manner that permits individual estimates to derive strength from the group effects (Efron & Morris, 1973). Using these estimates for each student at each assessment point, we categorized all students based on thresholds derived from normative data sets or common-sense scale values on measures. For the COSS-P, COSS-T, HPC, and HPQ-T, thresholds were set at one-half standard deviation below/above the mean of the normative sample to indicate performance within the normal range (for normative information, see masked for review; [name] et al., 2006; [name] et al., 2007), as this corresponds with a medium effect size. For the ACES and APS, threshold values were set at a value reflecting performance at the standard for grade level (3.0) or above. For academic grades, the threshold was set at a value of 3.0 or above.

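### Normal-range shares counted from empirical Bayes point estimates misstate each arm's percentage; the effect on any arm difference depends on where the cut-off lies

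*SAP*

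**What the plan says.** The SAP (Data Management and Analysis) forms a predicted score for each student at each assessment: the model's expected value plus predicted random effects for student and school. It says that these predictions "combine individual measures with group-level expected values in a manner that permits individual estimates to derive strength from the group effects", and defends them on the ground that "Statistical theory suggests that model-based predictions provide better estimates of true values than the actual data". The predictions are then dichotomised: "we categorized all students based on thresholds derived from normative data sets or common-sense scale values on measures". With HPC, HPQ-T and both COSS versions, "thresholds were set at one-half standard deviation below/above the mean of the normative sample to indicate performance within the normal range". For ACES, APS and academic grades the cut-off is 3.0.

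The SAP describes the expected value as the average of the whole group. The fixed part of the model is nevertheless arm-specific: "All models included time (as splines), treatment, and time-by-treatment interactions". Students also have "a random intercept and random slope for student to allow for variation in the effect of treatment assignment across students over time". The target of the shrinkage is thus the mean curve of the student's own arm, shifted by the school effect.

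For this step the SAP mentions no use of the posterior variance, no correction for reduced spread and no sensitivity analysis. It does not say how the categories will be summarised or compared between arms.

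**The concern.** The SAP's defence is right for its own question: an empirical Bayes prediction has a smaller expected squared error for one student's score than the raw score has. That does not carry over to the share of students past a cut-off. As a set, the predictions vary less than the true scores, and a share past a threshold depends on that spread. Each arm's percentage is therefore pushed away from 50%, toward the side its own mean lies on.

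At stake is how any normal-range percentages are read. A reader would take them as estimates of how many students truly reach the normal range in each arm, and would naturally subtract one from the other.

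**Working it through.** The documents state no normal-range percentage, so there is no figure to reproduce. The check is a closed-form calculation under stated assumptions.

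**Inputs from the documents**
- Within-student correlation r = 0.5, 0.6, 0.7 (protocol 6.1.4).
- At most m = 4 assessments per student (protocol 6.1.4).
- Effect 0.5 SD (protocol 6.1.4 and 6.2.2).

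**Assumptions**
- Scores are oriented so that higher is better, with a cross-sectional SD of 1.
- Random-intercept model: the true score is normal about its arm mean with variance r.
- The cut-off lies a distance g above the TAU mean. This is not in the documents, so g from 0 to 1.5 SD is examined.

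**Formulas**
- Reliability of a student's mean of m scores: rel = m·r / (1 + (m − 1)·r).
- Variance of the empirical Bayes values within an arm: r·rel, which is below r.
- True share past the cut-off, for arm mean μ and cut-off c: Φ((μ − c)/√r).
- Share counted from empirical Bayes values: Φ((μ − c)/√(r·rel)).

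**Worked case: r = 0.5, m = 4, g = 0.25**
- rel = 2.0/2.5 = 0.80, so the SD falls from √0.5 = 0.707 to √0.4 = 0.632.
- TAU: true Φ(−0.25/0.707) = 36.2%; counted Φ(−0.25/0.632) = 34.6%.
- OST: true 63.8%; counted 65.4%.
- Difference: true 27.6 points; counted 30.7.

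**Four scores per student** (TAU/OST in %; differences in points, taken before rounding)

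| g (SD) | r | True shares | True diff. | Counted shares | Counted diff. | Error |
|---|---|---|---|---|---|---|
| 0.25 | 0.5 | 36.2/63.8 | 27.6 | 34.6/65.4 | 30.7 | +3.1 |
| 0.25 | 0.7 | 38.3/61.7 | 23.5 | 37.7/62.3 | 24.7 | +1.2 |
| 0.5 | 0.5 | 24.0/50.0 | 26.0 | 21.5/50.0 | 28.5 | +2.5 |
| 0.5 | 0.7 | 27.5/50.0 | 22.5 | 26.5/50.0 | 23.5 | +1.0 |
| 1.0 | 0.5 | 7.9/24.0 | 16.1 | 5.7/21.5 | 15.8 | −0.3 |
| 1.0 | 0.7 | 11.6/27.5 | 15.9 | 10.4/26.5 | 16.0 | +0.1 |
| 1.5 | 0.5 | 1.7/7.9 | 6.2 | 0.9/5.7 | 4.8 | −1.4 |
| 1.5 | 0.7 | 3.6/11.6 | 7.9 | 3.0/10.4 | 7.5 | −0.4 |

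At g = 0 the differences equal those at g = 0.5, by symmetry. Results for r = 0.6 lie between (27.3 against 25.3 at g = 0.25; 6.3 against 7.2 at g = 1.5).

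**Fewer scores.** At r = 0.5 and g = 0.25, against a true 27.6, the counted difference is 33.5 if every student had two scores and 38.3 if every student had one. At g = 1.5, against a true 6.2, it is 3.7 and 2.1.

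**Random slopes and dropout.** A simulation used visits at weeks 0, 14, 22 and 55, 15% dropout, r of about 0.5 and an assumed slope variance. At 12 months the difference was 32.7 against 27.7 true at g = 0.25, and 4.1 against 6.1 at g = 1.5.

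**No treatment effect.** In the same simulation at g = 0.5, both arms were counted at about 20% against a true share of about 24%. The arm difference stayed near zero.

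**The case against.** The strongest reply has four parts.

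1. **The bias has no fixed direction.** Students are referred because they struggle most with these skills (protocol 3.4.5), and the normative cut-off is only half an SD from the normative mean. A cut-off beyond both arm means is therefore plausible, and there the arm difference is about right or understated. This stands. A reader might infer that the SAP's method inflates the benefit, or creates a responder difference from nothing. The documents do not support that: the cut-off's position is unknown, and with no effect and similar shrinkage in both arms the difference stays near zero. Similar shrinkage is itself an assumption, since the SAP reports that assessment timing varied by arm.

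2. **The summary is secondary.** The SAP's main estimate is the difference in change of model means, and Cohen's d is built on the same means. This stands. A reader might also infer that the percentages will be a headline result, but the SAP says only that students are categorised. An arm comparison is the natural use, not a stated one.

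3. **Raw scores are no better.** This also stands. Measurement error over-spreads them: at r = 0.5 and g = 0.25, single observed scores give a difference of 19.7 against 27.6. But the choice is not only between these two, because the same fitted model yields the share directly.

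4. **The remedy leans on the model.** Posterior probabilities depend on normality and on estimated variance components, whereas the scores are bounded item means analysed with weights. This is a fair limit, to be stated with the result. Empirical Bayes values come from the same model, so it is no reason to prefer counting them.

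**Conclusion.** The concern holds for the percentages. Thresholding these point estimates misstates the share in the normal range for any arm whose mean is not at the cut-off. For an arm difference, the error is upward with the cut-off at or between the arm means, about nil near 1 SD above the TAU mean (for a 0.5 SD effect), and downward further out. With four scores, r from 0.5 to 0.7 and random intercepts, it runs from about 3 points too high to 1.4 points too low. It is larger where students have fewer scores, and they too are categorised.

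These sizes are illustrations: the cut-off distances are assumed, and the SAP's model is richer than the one used here. This is a worthwhile correction to a descriptive summary and does not call the main efficacy analysis into question.

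**What to change.** Replace the counts with an average. From the same fitted model, compute each student's posterior probability of being beyond the threshold at each assessment time, using the posterior mean and variance or posterior draws, and average it by arm. Under the model, the average of P(true score beyond c | data) equals P(true score beyond c), so neither the under-spread of empirical Bayes values nor the over-spread of raw scores enters.

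The SAP should also:
- keep empirical Bayes values for individual-level display only;
- state that the proportions rely on the model's normality and variance components;
- give an interval that respects school clustering, for example a school-level bootstrap, noting that about 20 schools (protocol 8.1.1) make such an interval rough.

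The cost is a short SAP change and a little more coding, with no new data. Students no longer receive a simple yes/no label.
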